and increasing outflow of aqueous humor through the uveo-scleral pathway (Yamaji et al., 2005). Very recently, Fuwa et al., demonstrated that DE-117 lowers the IOP through a novel mechanism of action: that is, through both conventional and uveoscleral outflows (Fuwa et al., 2017). Currently approved IOP-lowering medications such as latanoprost (Latanoprost Ophthalmic Solution, 0.005%; NDA 20-597) lower IOP by enhancing uveoscleral outflow only, but do so through effects on a receptor for PGF2 $\alpha$ . Unlike latanoprost and other approved prostaglandin F receptor (FP) agonists that are synthetic prostanoid analogues, DE-117 is a non-prostanoid chemical compound.

To date, Santen has completed seven clinical studies including three clinical studies (33-001, 33-002, 33-003) in the U.S. and four clinical studies (01171502, 01171503, 01171504, 01171506) in Japan with DE-117 in healthy adult subjects, or subjects with OAG or OHT to evaluate the efficacy and safety of DE-117. DE-117 Ophthalmic Solution 0.002% appeared to be well tolerated and efficacious in IOP lowering. As a result, it was chosen to advance into the phase III clinical development program in the US.

Additional information on DE-117 Ophthalmic Solution, including the results of nonclinical and clinical studies can be found in the Investigator's Brochure.

The proposed study is a randomized, double-masked, active-controlled, parallel group, multi-center, Phase III study. The total duration of treatment is 3 months. The objective is to investigate the efficacy and safety of DE-117 Ophthalmic Solution 0.002% compared with Timolol Maleate Ophthalmic Solution 0.5% in subjects with glaucoma or OHT.

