#### **12.1.3. Events of Special Interest**

The following are considered ESIs and should be reported on the appropriate eCRF with as much information as available within 24 hours of knowledge of the event:

- Pregnancy:
  - There are no controlled data with the investigational product in human pregnancy. It is required that females of childbearing potential use effective contraception during the study and recommended for 4 weeks for female subjects of childbearing potential and 12 weeks for male subjects capable of fathering children after the completion of the study. Any pregnancy occurring during study treatment should be reported and the subject will be discontinued from the study. The subject should be followed until the end of pregnancy or until the end of the study, whichever is longer.

- Medication administration errors
  - Study medication administration errors determined to be **significant** by the Investigator will be reported and evaluated as ESIs. Examples of study medication administration errors may include, but are not limited to: incorrect dose of study medication and administration of study medication from an incorrect kit. An AE does not necessarily need to have occurred to count as a study medication administration error. A medication administration error is an unintended failure in the process of treatment with a medicinal product that leads to, or has the potential to lead to harm of the subject.
- Macular edema (including cystoid macular edema):
  - Macular edema has been reported in some patients during the DE-117 clinical trials. Any cases of macular edema (including cystoid macular edema) should be reported in the ESI form in eCRF, or in case the EDC system is down, in the manual ESI form. Any cases of macular edema (including cystoid macular edema) will need to be followed until the event is determined to be resolved, irreversible, chronic, stable, the subject withdraws consent, or no further information can be reasonably obtained as per [Section 12.1.4](#).

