#### 12.1.4. Follow-up of Adverse Events

All reported AEs should be followed until resolution or until the subject's participation in the study ends. Subjects with the following types of events should be followed by the Investigator until the event is determined to be resolved, irreversible, chronic, stable, the subject withdraws consent, or no further information can be reasonably obtained.

- On-going SAEs issued after study medication treatment
- On-going ESIs, including pregnancy, medication errors resulting in AE's, and macular edema/cystoid macular edema issued after study medication treatment
- Early termination and withdrawal from the study due to study medication related AEs

In addition, on a case by case basis, Santen (or designee) may request follow up beyond the scheduled exit visit.

The follow-up information on an individual SAE or AE (or ESI) will be entered into the eCRF prior to database lock. If the information requested by Santen is not part of the eCRF, or when database lock has already been completed, the site's response to follow-up requests should be emailed to [[contact]](mailto:[contact]) or reported in writing and fax to [contact] (in the US).

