9.1.2. Macular Edema

Subjects who developed AEs during the study with one of the following preferred terms will be included in the macular edema summary:

- Macular edema
- Cystoid macular edema

Macular edema start time (in terms of study day) and duration of the AE will be summarized using mean, standard deviation, median, minimum, and maximum by study eye and fellow eye separately. To allow for the computation of simple descriptive statistics, only subjects who develop macular edema during the study will be used for the macular edema start time summary, and only subjects who develop these AEs during the study and later resolved will be used in the duration of AE analysis.

Change from baseline in BCVA at the onset of macular edema, when macular edema is resolved, and at the last visit will be summarized using mean, standard deviation, median, minimum, and maximum by study eye and fellow eye separately. Subjects with pseudophakic lens or phakic lens at baseline who developed macular edema during the study will be summarized by frequency and percentages separately.

The aforementioned summaries will be performed at the eye level. All macular edema AEs will be provided in a listing.

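### Duration of macular edema and ocular inflammation is summarised for resolved events only, so it reads short whenever any event is unresolved

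*SAP*

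**What the plan says.** SAP 9.1.2 (Macular Edema) states that "duration of the AE will be summarized using mean, standard deviation, median, minimum, and maximum by study eye and fellow eye separately". It then restricts the data: "only subjects who develop these AEs during the study and later resolved will be used in the duration of AE analysis". The reason given is convenience: "To allow for the computation of simple descriptive statistics". SAP 9.1.1 (Ocular Inflammation) applies the same restriction for the same reason. Neither section plans a censored-data estimate, and neither asks for the number of unresolved events beside the duration. Under SAP 6.2.3 (Table 5), an event with a completely missing resolution date counts as ongoing, so it also leaves the duration summary.

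Follow-up differs between the two event types. Protocol 12.1.4 sets the general rule: "All reported AEs should be followed until resolution or until the subject's participation in the study ends". Ongoing events of special interest, which include macular edema, are followed longer, "until the event is determined to be resolved, irreversible, chronic, stable, the subject withdraws consent, or no further information can be reasonably obtained". Follow-up information "will be entered into the eCRF prior to database lock". Ocular inflammation is not among the events of special interest in SAP 4.4.1.4. It gets the longer follow-up only if it is an SAE or a drug-related event leading to withdrawal, or if the sponsor asks for it case by case.

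**The concern.** Entry to the summary depends on the quantity being summarised. At any given length of observation, a longer event is less likely to have ended, so removing unresolved events removes long durations preferentially. The mean, median and maximum all move down.

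Macular edema is the only disease on the list of events of special interest, and Protocol 12.1.3 notes that "Macular edema has been reported in some patients during the DE-117 clinical trials". How long such an event lasts is a natural question for a safety reader, and this table is where the answer will be sought. The safety objective is also comparative. If events last longer in one arm, that arm loses more of them from its summary, so a difference between arms is compressed.

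**Working it through.** The documents state no event rate, duration or resolution rate, so there is no plan figure to reproduce. The direction follows from the rule. The size can only be illustrated.

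**From the documents.** "The total duration of treatment is 3 months", with Visit 5 at Day 91 ± 7.

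**Assumed (not in the documents).** Onset is uniform over Days 1 to 91, a span of L = 90 days. Duration D is exponential with true mean μ = 30, 60 or 90 days. Observation ends a days after Day 91, with a = 0 or 90. The time available to observe resolution, C, is then uniform on (a, a + L).

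**Formulas.**
- Fraction unresolved: U = (μ/L)[e^(−a/μ) − e^(−(a+L)/μ)]
- Resolved-only mean: M = {μ − (μ/L)[(a+2μ)e^(−a/μ) − (a+L+2μ)e^(−(a+L)/μ)]} / (1 − U)

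**Worked case, μ = 60, a = 0.** e^(−1.5) = 0.2231. U = (60/90)(1 − 0.2231) = 0.518. The numerator of M is 60 − (60/90)(120 − 210 × 0.2231) = 11.24. M = 11.24/0.482 = 23.3 days, which is 39% of the true 60.

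| True mean (days) | Observation ends | Excluded | Resolved-only mean (days) | Share of truth |
|---|---|---|---|---|
| 30 | Day 91 | 32% | 18.3 | 61% |
| 60 | Day 91 | 52% | 23.3 | 39% |
| 90 | Day 91 | 63% | 25.4 | 28% |
| 30 | 90 days later | 2% | 28.1 | 94% |
| 60 | 90 days later | 12% | 43.8 | 73% |
| 90 | 90 days later | 23% | 51.4 | 57% |

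The table entries come from a simulation of 400,000 events per row, and the formulas agree with them. In the same runs, total observed event time divided by the number resolved, which uses the ongoing events as censored, returned the true mean to within 0.3 days in every row.

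**Medians.** The median is affected too. At Day 91 the resolved-only medians are 13.8, 18.8 and 21.0 days, against true medians of 20.8, 41.6 and 62.4.

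**Comparison between arms.** With observation to Day 91, true means of 30 and 90 days read as 18.3 and 25.4. A threefold difference appears as 25.4/18.3 = 1.4-fold.

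**Follow-up complete, but the longest events closed as chronic or irreversible.** If the longest fraction q of exponential durations is dropped, the remaining mean is 1 + q ln(q)/(1 − q) times the truth. This gives 84%, 74%, 60% and 48% for q = 5%, 10%, 20% and 30%. Longer follow-up therefore does not remove the bias if some events never resolve.

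**The case against.** The strongest reply concerns size. For macular edema the Day 91 cut-off is the wrong model, because the protocol follows ongoing cases past exit and takes the information into the eCRF until database lock. With short events or long follow-up the bias nearly vanishes. A true mean of 30 days reads as about 28 with 90 more days, and a true mean of 60 days reads as 54.4 (91%) with 180 more days. If every event resolved before lock there would be no bias. This stands, and the Day 91 rows should not be quoted for macular edema. What remains is that its follow-up may end without resolution, and those events are still excluded.

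A second reply is that the unresolved events are not hidden. They stay in the incidence tables (SAP 9.1), the start-time summaries, the full listings and, for macular edema, the summary of BCVA change at the last visit. The restriction is stated openly, and no safety testing is planned (SAP 6). This limits the consequence. It does not correct a mean or median that readers will take as the duration of the event.

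A third reply is that few events are likely. There are about 200 subjects per arm over 3 months, and Protocol 8.2 excludes a history of macular edema, its known risk factors, iritis or uveitis. A Kaplan-Meier median may then not be estimable. That is fair, and it is a reason to put the counts first.

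A reader might infer that the plan will substantially understate the duration of the drug's main safety concern, or overstate its reversibility. The documents do not support either reading. They rank no event as the main concern, and ocular inflammation is not an event of special interest. The duration summary does not estimate the proportion resolving. Nor is every ongoing event a long one, since under uniform onset some are open only because they began late.

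**Conclusion.** The point holds as a bias of known direction and unknown size in two descriptive safety summaries. Whenever any event is unresolved, the rule in SAP 9.1.1 and 9.1.2 tends to shorten the reported duration. Under the assumptions above (uniform onset, exponential durations, true mean 30 to 90 days), the resolved-only mean is about 28% to 61% of the truth if observation stops at Day 91. This fits ocular inflammation better, which has no routine extended follow-up. With 90 more days it is about 57% to 94%, which is closer to macular edema. The 90 days is itself an assumption, since the documents do not give the time to database lock. Confidence is high for the direction and low for the size. No incidence figure, hypothesis test or efficacy conclusion changes.

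**What to change.** In SAP 9.1.1 and 9.1.2:

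- Report the number of events resolved and ongoing per arm, at the eye level already used for these summaries. Show events closed as chronic, irreversible or stable within the unresolved count.
- Summarise duration by the Kaplan-Meier method, with ongoing events censored at last follow-up, where counts allow. Otherwise rely on the listing.
- Label any resolved-only statistic that is kept as applying to resolved events only, and print it beside the number ongoing.

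The cost is a change of SAP wording and minor programming. Event dates and outcome are already recorded under Protocol 12.1.1.2, so no new data or visits are needed. The downside is that the median may not be estimable with few events. In addition, when follow-up stops because an event was judged irreversible, censoring at that date is informative, which is why those events need their own count.

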9.1.3. Cosmetic Change(s)

Subjects who developed AEs during the study with one of the following preferred terms will be included in the cosmetic change summary:

- Blepharal pigmentation
- Eyelash changes
- Eyelash hyperpigmentation
- Eyelash thickening
- Growth of eyelashes
- Lid sulcus deepened
- Trichiasis
- Iris hyperpigmentation

Other preferred terms might be added upon review of the AE data before database lock.

Cosmetic change(s) start time (in terms of study day) will be summarized using mean, standard deviation, median, minimum, and maximum by study eye and fellow eye separately. To allow for the computation of simple descriptive statistics, only subjects who develop cosmetic change(s) during the study will be used for the cosmetic change start time summary.

The aforementioned summaries will be performed at the eye level. All cosmetic change AEs will be provided in a listing.

9.2. Best-Corrected Visual Acuity

BCVA (logMAR scores) and changes from baseline will be summarized by treatment and analysis visit for study eyes and fellow eyes, separately. In addition, any change (worsening or improvement) of ≥ 0.2 LogMAR (2 lines) from baseline will be summarized and listed.

9.3. Slit-lamp Biomicroscopy

For each biomicroscopy parameter, frequency and percentage of rating scores will be summarized by analysis visit for study eyes and fellow eyes, separately. In addition, any clinically significant worsening (increase) from baseline will be summarized and listed.

9.4. Ophthalmoscopy

Cup-to-disc ratio will be summarized with n, mean, standard deviation, median, minimum and maximum by treatment and analysis visit for study eyes and fellow eyes separately. In addition, subjects with at least 0.2 increase in cup/disc ratio from baseline will be listed.

Glaucomatous optic nerve findings will be assessed as 0 = none, 1 = mild, 2 = moderate, or 3 = severe. Frequency and percentage of rating scores will be summarized by treatment and analysis visit for study eyes and fellow eyes, separately. In addition, subjects with any worsening (increase) of ≥ 2 units from baseline will be listed.

Retina/Macula/Choroid and vitreous will be assessed as normal or abnormal. Shift from baseline at Month 3 will be summarized by treatment on study eyes and fellow eyes separately. In addition, subjects with change from baseline from normal to abnormal in these parameters will be listed.

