### **Diseases**

13. Presence of advanced glaucoma (e.g., visual field mean deviation worse than -12 dB) in either eye.
14. Presence of any corneal abnormality or other conditions interfering with or preventing reliable Goldmann applanation tonometry (e.g. Fuch's dystrophy or significant corneal surface abnormality) in either eye.
15. Presence of any active severe external ocular disease, inflammation, or infection of the eye and/or eyelids in either eye.
16. Presence or history of macular edema or known risk factors for macular edema in either eye.
17. History of severe ocular trauma in either eye.
18. History of iritis and/or uveitis in either eye.
19. History of retinal detachment, proliferative diabetic retinopathy, or any retinal disease that may be progressive during the time course of the study in either eye.
20. Presence or history of any disease or condition that in the opinion of the study Investigator may put the subject at significant risk, may confound study results, or may interfere significantly with the subject's participation in the study (e.g., recurrent corneal erosion syndrome, uncontrolled cardiovascular disease etc.).
21. Any decision by the Investigator or Medical Monitor to terminate a subject in screening or declare any subject ineligible for any sound medical reason.

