#### **Glaucomatous Optic Nerve Findings**

The optic nerve will be evaluated using a 4-point scale (0-3 scale).

- |          |       |  |
|----------|-------|--|
| None     | (0) = | No damage  |
| Mild     | (1) = | Optic nerve damage, secondary to glaucoma including any rim loss (sloping or thinning) |
| Moderate | (2) = | Optic nerve damage, including cupping to disc margin at one or more points             |
| Severe   | (3) = | Optic nerve damage, nearly total cupping, only nasal rim or less present               |

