7.2. Demographics and Baseline Characteristics

Subject demographics and baseline characteristics will be descriptively summarized for the FAS by planned treatment. Specifically, for subject demographics, the following variables will be summarized:

- Age at randomization (continuous and categorical: < 65 years or \geq 65 years)
- Sex (categorical: Male or Female)
- Ethnicity (categorical: Hispanic/Latino or Not)
- Race (categorical: American Indian or Alaska Native, Asian, Black or African American, Native Hawaiian or Other Pacific Islander, White, or Other)

For baseline characteristics, the following variables will be summarized for study eye and fellow eye, separately:

- Primary ocular diagnosis (categorical: POAG, Pseudoexfoliative Glaucoma, Pigmentary Glaucoma, or OHT)
- Iris Color (categorical: Blue/Gray, Blue/Gray with Slightly Brown, Blue/Gray – Brown, Green, Green with Slightly Brown, Green – Brown, Yellow – Brown, or Brown)
- Prior use of IOP-lowering medications (categorical: oral/topical carbonic anhydrase inhibitors, alpha agonists, beta-blockers, prostaglandin/prostaglandin analogues, or none)
- Prostaglandin naive (Yes or No)
- Baseline lens status (categorical: phakic or pseudophakic/aphakic)
- Baseline mean diurnal IOP score and baseline IOP score at each scheduled timepoint (08:00, 10:00, and 16:00)
- BCVA (logMAR)
- Central corneal thickness (μ m)
- Glaucomatous optic nerve findings (categorical: none, mild, moderate, or severe)

- Anterior chamber angle classification (Shaffer scale; categorical: approximately 5 degrees or less, approximately 10 degrees, approximately 20 degrees, approximately 30 degrees, or approximately 40 degrees or more)
- Visual field (parameters: glaucoma Hemifield test, visual field mean deviation by device, and visual field pattern standard deviation by device)

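### The optic-nerve listing cannot flag a grade 2 eye or any one-grade worsening, and SAP 9.4 omits the change-from-baseline summary that Protocol 14.8 promises

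*SAP*

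**What the plan says.** Protocol 21.3.12 sets a four-point optic-nerve scale, and SAP 9.4 repeats it: "Glaucomatous optic nerve findings will be assessed as 0 = none, 1 = mild, 2 = moderate, or 3 = severe".

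SAP 9.4 plans two outputs for this grade:

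- A table: "Frequency and percentage of rating scores will be summarized by treatment and analysis visit for study eyes and fellow eyes, separately".
- A listing: "subjects with any worsening (increase) of ≥ 2 units from baseline will be listed".

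The same section treats its other variables differently. For cup/disc ratio, besides descriptive statistics, "subjects with at least 0.2 increase in cup/disc ratio from baseline will be listed". For retina/macula/choroid and vitreous, "Shift from baseline at Month 3 will be summarized by treatment on study eyes and fellow eyes separately", and any change from normal to abnormal is listed.

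The protocol asks for more on the nerve grade. Section 12.2.1 names the glaucomatous optic nerve as the ophthalmoscopy variable. Section 12.2 says that changes from baseline will be evaluated. Section 14.8 says that such changes in the 12.2.1 parameters will be summarized by treatment. SAP section 10, which records additions and changes to the protocol's analyses, has three entries (analysis set, key secondary endpoint, sensitivity analysis). None concerns ophthalmoscopy.

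**The concern.** A threshold of two grades on a scale that ends at three leaves part of the scale out of reach. An eye that starts at grade 2 has only one step left, so it cannot meet the rule however it progresses. First onset of damage (0 to 1) and progression to the worst grade from the one below it (2 to 3) also go unlisted.

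This would matter less if another table tied each eye's Month 3 grade to its own baseline, but SAP 9.4 plans none for this variable. Visual field is scheduled only at Visit 1, so the scheduled Month 3 information on glaucomatous damage is the nerve grade and the cup/disc ratio. At stake is whether a reader of the study report can see one-grade worsening by arm, particularly in eyes that already have moderate damage.

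**Working it through.** The plan states no figure to reproduce here. The check is an enumeration, followed by a comparison of sections.

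**Inputs.** Scale 0, 1, 2, 3 (Protocol 21.3.12, SAP 9.4). Listing rule: follow-up grade minus baseline grade of at least 2 (SAP 9.4). Baseline is the Visit 2 measurement (SAP 4.2.2).

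**Step 1: largest possible rise, 3 − baseline grade.**

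| Baseline grade | Largest rise | Can reach 2? |
|---|---|---|
| 0 | 3 − 0 = 3 | yes |
| 1 | 3 − 1 = 2 | yes |
| 2 | 3 − 2 = 1 | no |
| 3 | 3 − 3 = 0 | no; the scale has no higher grade |

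**Step 2: all upward moves.**

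| Move | Rise | Listed now | Listed if any worsening to grade 3 is added |
|---|---|---|---|
| 0 to 1 | 1 | no | no |
| 0 to 2 | 2 | yes | yes |
| 0 to 3 | 3 | yes | yes |
| 1 to 2 | 1 | no | no |
| 1 to 3 | 2 | yes | yes |
| 2 to 3 | 1 | no | yes |

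The current rule lists 3 of 6 moves and omits every one-grade move. The extended rule lists 4 of 6, and a grade 2 eye becomes listable. The remaining two moves, 0 to 1 and 1 to 2, would appear by arm in a shift table, which shows all six. These are counts of kinds of move. They say nothing about how often each occurs.

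**Step 3: what the frequency table can show.** Take an illustrative arm with 50 eyes at each grade at baseline (not a figure from the documents). Suppose ten eyes go from 2 to 3 and ten are read as 3 then 2.

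- Grade 2 at Month 3: 50 − 10 + 10 = 50.
- Grade 3 at Month 3: 50 + 10 − 10 = 50.

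The table reads 50/50/50/50 at both visits, and the listing is empty. Safety summaries use observed data only (SAP 6.2.2), so missing examinations can also mask change: if one grade 3 eye has no Month 3 examination and one grade 2 eye moves to 3, the grade 3 count stays at 50.

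**Step 4: protocol against SAP.** Protocol 14.8, through 12.2.1, calls for a change-from-baseline summary of this grade by treatment. SAP 9.4 specifies neither a change table nor a shift table for it. SAP section 10 neither withdraws the commitment nor explains the difference.

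**The case against.** The listing is a supplement, and a higher threshold for naming individual subjects can be defended. SAP Table 1 specifies dilation at Visits 1 and 5 but not at Visit 2, which is the baseline. Some one-grade differences may therefore reflect how the nerve was examined, or grader variation, and a listing of every one-grade rise would collect them. This stands. It is a reason not to list every such rise, but it does not answer the ceiling at grade 2 or the missing shift table. Both arms follow the same examination schedule, so comparing arms puts such shifts in context.

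Other routes remain: cup/disc ratio summaries and their listing, adverse events (Protocol 12.1.1 allows for clinically significant worsening of an existing condition), and progressive disease as a discontinuation reason, which SAP 7.1 tabulates. This also stands, in part. None of these is tied to the nerve grade. The cup/disc listing has its own ceiling: the ratio cannot exceed 1.0, so an eye above 1.0 − 0.2 = 0.8 at baseline cannot qualify.

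The cancellation example needs some eyes to be graded lower at Month 3, which would itself be grading variation. That is fair. If no eye were graded lower and the same eyes were seen at both visits, the margins and the listing together would give the one-grade counts by arm. The plan cannot guarantee either condition, and even then the eyes would not be identified.

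Two stronger readings are tempting, and the documents do not support them.

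- A reader might infer that many grade 2 and 3 eyes are expected because SAP 7.2 prints moderate and severe at baseline. That table prints whole scales. It also prints the two narrowest Shaffer angle categories, although Protocol 8.1 requires grade 2 or above. Nor does eligibility turn on visual field alone: the exclusion reads "Presence of advanced glaucoma (e.g., visual field mean deviation worse than -12 dB) in either eye", where the field value is only an example. No nerve-grade limit is stated, so grade 2 eyes are not barred by number, but how many enrolled is unknown.
- A reader might infer that the trial could report no optic-nerve worsening while damaged eyes progress. The listing could be empty in that case. The frequency table would still show a net rise in grade 3, and the routes above remain.

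**Conclusion.** The point holds as a gap in one descriptive safety output. The ceiling at grade 2 and the omission of all one-grade moves follow from the scale and the rule alone and need no assumption. The SAP is also silent on a change-from-baseline summary that the protocol promises. That is best read as an undeclared omission: nothing in SAP section 10 shows a decision to drop it.

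The weight is minor. SAP section 6 plans no statistical testing of safety measures, and no efficacy result, error rate or power figure depends on this output. The number of eyes affected cannot be stated, because the documents give neither the baseline grade distribution nor a rate of one-grade change over three months.

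**What to change.** In SAP 9.4:

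1. Add a table of baseline grade by Month 3 grade for the glaucomatous optic nerve, by treatment, for study eyes and fellow eyes separately, in the form already planned for retina/macula/choroid and vitreous. This also meets the commitment in Protocol 14.8.
2. Extend the listing to any worsening to grade 3, in addition to increases of 2 or more grades.
3. Add a note that Visit 2 is not specified as dilated while Visit 5 is, so one-grade shifts should be interpreted by comparing the arms.

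The cost is a few sentences in the SAP, one extra table and a slightly longer listing, all from data already scheduled for collection. The downside is that some one-grade shifts will be grader variation or a dilation effect. The comparison between arms addresses this, and 0-to-1 and 1-to-2 shifts would appear as counts in the table without being listed by subject.
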